4.3 Exclusion criteria

For this study exclusion criteria are set for GP practices and for participating patients.

Participants:

- The patient is terminal.
- The patient is living in a residential home.
- The patient has dementia or a disability that prevents them from communicating effectively. The patient already has experience with the positive health tool.
- The patient is not competent to make decisions concerning their health. This will be assessed by the patient's own general practitioner.
- Veto of the GP

Exclusion criteria for GP practices:

- Veto of GP
- The GP or POH-GGZ is already participating in this study in a different cluster.

4.4 Sample size calculation

Sample size calculation for a stepped wedge cluster RCT is performed using the formule of De Hoop et al (Woertman et al., 2013). The unadjusted sample size for a RCT was established on 380, 190 per arm, based on average one year Health Insurance Act spending of a mean of ca €22.494 (€24.585SD)(source Statistics Netherlands), with 80% power, 5% alpha, 2-sided Equality and 25% decrease. The design effect for this study is 0.54. This is based on 1 baseline measure, 4 steps, and ICC of 0.1, 10 patients per cluster and a lost to follow-up of 20%. This leads to a sample side of 204 patients. Rounded off, we will include 200 patients divided over 20 clusters.

TREATMENT OF SUBJECTS

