A stepped-wedge cluster randomised controlled trial (RCT) design will be used. This study will be performed in 20 general practices that do not yet offer proactive integrated care for hotspotters. Data on cost-effectiveness will be quantitatively assessed. Patient experience will be qualitatively assessed through focus groups and quantitative using validated questionnaires. Besides, the process will be both qualitatively and quantitatively evaluated using interviews or focusgroups, observations (audio recording) with care professionals on common themes of process evaluation and a validated questionnaire.

Study population:

In total 200 hotspotters will be included. Hotspotters are individuals with at least two incidents of acute care utilisation (defined as out-of-office GP consultations, acute psychiatric care, emergency department visits and unplanned admissions) during the past year, and problems on two out of three health domains (chronic somatic, mental and/or social problems) based on diagnosis (coded with the International Classification of Primary Care) or medication

(ATC) coding.

Intervention:

The proactive integrated care intervention that will be used consists of five steps:

1. Active invitation of the patient from the practice.
2. Consult of 45 minutes with a trained Practice Nurse Mental Health Care based on the Positive Health Methodology.
3. Multidisciplinary team meeting based on the spider web with domain specific explanation to create a personalised care plan and assign a care coordinator to each patient.
4. Execution of the personalised care plan and frequent pro-active contact between care coordinator and the patient. In the first 12 weeks there is a minimum of 3 contact moments, however more frequent contact is expected. The proactive nature of this contact is emphasized.
5. Follow-up of the personalised care plan using clinical review and at least one multidisciplinary meeting. If needed, ad hoc additional meetings can be organised.

Nature and extent of the burden and risks associated with participation, benefit and group relatedness:

Participation in this study is expected to be low risk for the patients. However, both risks and benefits are associated with participation.

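### The sample size does not follow from its own inputs: a 25% decrease needs about 300 per arm, not 190, and the 20% loss adds no patients, so 200 patients give about 51-59% power, not 80%

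*Protocol*

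**What the plan says.** Section 4.4 of the protocol bases the calculation on "average one year Health Insurance Act spending of a mean of ca €22.494 (€24.585SD"), "with 80% power, 5% alpha, 2-sided Equality and 25% decrease". From these it reports: "The unadjusted sample size for a RCT was established on 380, 190 per arm".

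It then moves to the stepped-wedge design: "The design effect for this study is 0.54". The inputs listed for that step are one baseline measure, four steps, an ICC of 0.1, "10 patients per cluster and a lost to follow-up of 20%. This leads to a sample side of 204 patients". The 204 is rounded to 200 patients in 20 clusters, and the Summary repeats the target: "In total 200 hotspotters will be included".

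The section mentions no log scale, no adjustment for earlier costs and no other reduction of variance. Sections 5.5 and 5.6 say that patients who withdraw are not replaced and that their data collection stops.

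**The concern.** Every input for a plain two-arm comparison of means is printed, so the 190 per arm can be checked directly, and it looks far too small for a standardised difference of about 0.23. The 20% loss also appears among the inputs of the design effect rather than as an increase in the number enrolled, and 380 times 0.54 is already about 204.

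This is the only power statement in the protocol. Costs are one half of the primary outcome, incremental cost-effectiveness. If the 80% is not delivered, a true 25% reduction in spending would be missed about half the time, and an inconclusive cost result would be judged against a power that the trial never had.

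**Working it through.** **Inputs (all from section 4.4).** Mean €22,494; SD €24,585; decrease 25%; two-sided alpha 5% (z = 1.960); power 80% (z = 0.842); one baseline measure, k = 4 steps, ICC r = 0.1, n = 10 per cluster, loss 20%. One measurement per step is assumed, because the section does not state it.

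**Step 1: the unadjusted size.**
- Difference: 0.25 × 22,494 = €5,623.5. Standardised: 5,623.5 / 24,585 = 0.229.
- n per arm = 2 × (1.960 + 0.842)² × (24,585 / 5,623.5)² = 300.0, so 600 in total. A two-sample t-test gives 301 per arm.
- Plan: 190 per arm, 380 in total. This is not reproduced.
- Power at 190 per arm: Φ(0.2287 × √(190/2) − 1.96) = 60.6%.
- For 190 per arm to give 80% power, the decrease would have to be about 31%, or the SD about €19,560.

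**Step 2: other readings of the same inputs.**

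| Reading | n per arm |
|---|---|
| One-sided alpha | 237 |
| SD shrinking with the mean | 235 |
| Gamma model, log link | 227 |
| €22,494 read as the treated mean | 169 |
| Log-normal test | 149; divided by 0.8 = 186 |
| One-sample t-test | 152; divided by 0.8 = 190 |

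Only the last two come near 190, and only if the 20% loss is already inside it.

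**Step 3: the design effect.** The section names its formula without printing it. The usual form is [1 + r(kn + n − 1)] / [1 + r(kn/2 + n − 1)] × 3(1 − r) / [2(k − 1/k)].
- n = 10: (5.9 / 3.9) × 0.36 = 0.5446. This reproduces the 0.54. The generalised least squares variance of the stepped-wedge model with period effects agrees.
- n = 8 (10 less 20%): (4.9 / 3.3) × 0.36 = 0.5345.

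**Step 4: the 204 and the loss.**
- 380 × 0.54 = 205.2.
- With n = 8: 190 × 0.5345 = 101.6, rounded up to 102 per arm, gives exactly 204. The loss may therefore have entered as a smaller cluster size. That route lowers the requirement; it does not raise it.
- Allowing for loss in enrolment would give 204 / 0.8 = 255.

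**Step 5: what 200 patients give.** The equivalent number per arm is N / (2 × design effect); power is Φ(0.2287 × √(n/2) − 1.96); the detectable decrease is 2.802 × 24,585 × √(2/n) / 22,494.

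| Case | Equivalent n per arm | Power for 25% | Decrease with 80% power |
|---|---|---|---|
| 200 analysed, n = 10 | 200 / (2 × 0.5446) = 183.6 | 59% | 32% |
| 160 analysed, n = 8 | 160 / (2 × 0.5345) = 149.7 | 51% | 35% |

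**Step 6: what the stated target needs.** 600 × 0.5446 = 327 analysed, and 327 / 0.8 is about 408 enrolled. With n = 8, 600 × 0.5345 = 321 analysed and about 401 enrolled.

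**The case against.** The strongest defence is that a different calculation was done and not described. A log-normal test on the same mean and SD needs 149 per arm, or 186 after division by 0.8. On that scale, the equivalent sizes in step 5 (183.6 and 149.7 per arm) give about 87% and 80% power, so 200 patients with 20% loss would be enough. A gamma model with a log link gives about 71% and 62%. Section 6 plans multilevel generalised linear models and fixes no distribution or link for costs, so a raw-euro test is not prescribed there.

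This does not rescue the section as written. It gives an arithmetic mean and SD and no log scale. It calls the 380 unadjusted and lists the loss later, whereas this route needs the loss already inside the 380. A log-normal test also compares geometric means, while incremental cost rests on the difference in mean euros. The one-sample route reaches 190 exactly, but it is the wrong formula for two arms and leaves the shortfall in place.

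Two points stand:
- The loss is listed and may have been used as a smaller cluster size, so the exact criticism is that it does not increase enrolment.
- The design effect has no term for correlation within a patient, although the same patients are followed through control and intervention and three earlier years of cost data are available. The trial's actual precision may differ from these figures.

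**Conclusion.** The concern holds. The inputs in section 4.4 require 300 per arm, not 190, so the unadjusted figure is 37% too low (110 / 300), and the 20% loss adds no patients. The 0.54 design effect is sound; the error lies before it. As described, 200 patients give about 59% power without loss and 51% with 160 analysed, or 80% power for a decrease of 32% to 35%.

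The mismatch of 190 against 300 follows from the printed inputs alone. The power figures are conditional on a comparison of mean euros with a common SD, on one-year spending as the outcome, and on the protocol's own design effect.

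**What to change.** Rewrite section 4.4:
- Give the unadjusted requirement that follows from the stated inputs, 300 per arm (600 in total), with the formula.
- Keep the 200 patients and state what they provide: about 59% power for a 25% decrease, 51% after 20% loss, or 80% power for a decrease of 32% to 35%.
- Treat loss as division of the required number by 0.8, separately from the cluster size used in the design effect.
- If a log-scale or other method was in fact used, give that method, its inputs and the place of the loss instead of the figures above, and explain how it relates to the difference in mean costs.

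The cost is the rewording of one section and a less favourable stated power or detectable effect. Enrolment does not change.

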1. OBJECTIVES

The primary goal of this study is to get insight in the cost-effectiveness after 12 months of working with a proactive, integrated (social) care approach in patients fitting our definition of a hotspotter. A hotspotter is a patient with problems on two out of three health domains (chronic somatic, psychiatric and/or social) and at least 2 acute care activities in the previous 12 months. The medical data from 3 years prior to the start of the study will be used to analyse the costs and utilisation of care. This extended period used for data analysis was deliberately chosen to include a timeframe during and before the SARS-CoV-2 pandemic. Since it is yet unknown how the pandemic and its subsequent measures affected our population and their usage of care.

Hypothesis: We hypothesise that after one year of working with a proactive approach of integrated care to improve the care for patients with problems on two out of three health domains (chronic somatic, psychic and/or social) and at least 2 acute care activities in the previous 12 months will result in reduction in volume and spending of acute care, improvement in experienced health and in patient experience.

Research questions:

Is proactive integrated care cost-effective and result in better patients experience than usual care after 12 months for patients with problems on multiple life domains?

Primary outcomes: Incremental cost-effectiveness from a societal perspective. Information on cost will be based on patient-reported data obtained by questionnaires supplied with data from the GP medical files (*Huisarts informatie system, HIS*) and through CBS microdata. To assess the effectiveness the EQ-5D-5L will be used for determining quality of life.

Secondary outcomes:

Insight into patients experience of care:

Insights into the experiences of care will be gathered during a focus group and information about self-efficacy (PAM-13 and SE+IN itemlist), proactive coping (UPCC), and quality of life (SF-12) will be collected using questionnaires (Hibbard, Mahoney, Stockard, & Tusler, 2005; Bode, & de Ridder, 2008; Turner-Bowker, & Hoque, 2014). A questionnaire on experience of care has been considered, but no validated and appropriate questionnaires for this population are available. Therefore, for insight and rich information on the experienced care the format of a focus group was chosen.

Process evaluation:

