3. STUDY DESIGN

We will use a stepped-wedge randomised controlled trial (RCT) design (Hemming, Haines, Chilton, Girling, & Lilford, 2015). This design involves random and sequential crossover of groups from control to intervention until all groups are exposed to the intervention. A stepped wedge cluster RCT is especially useful when the intervention is thought to do more good than harm (i.e., when there is no equipoise). In that situation, it is unethical to withhold or withdraw the intervention from a proportion of the subjects as would occur in a parallel group or classic cluster RCT. Besides, it may be impossible to implement the intervention in half of all clusters simultaneously because of practical, logistical, or financial reasons, which is also the case in the current study with regard to the practical and logistical reasons. Then, the stepwise treatment implementation of the stepped wedge design offers a solution. Since all patients included in this study will be offered the intervention, which may contribute to limiting lost to follow-up

The personalized approach, local collaborations with the social domain and organizational differences between general practices will result in nuanced differences in how our intervention will be applied. Besides, training the Positive Health methodology and the enhanced collaboration between domains most likely effects patients not-offered the intervention as well. Randomisation will therefore be done by cluster.

This study will be performed in 20 general practices. Each practice will form one cluster. We aim to include an average of 10 patients per cluster. A GP or POH-GGZ can only participate in one cluster. The terms GP practice and cluster will be used alternatively and exchangeable from this point on, both referring to the given description.

Each participating patient starts with a control period and will cross-over to the intervention period. The control period varies between 2 to 8 months. All patients from a GP practice cross-over at the same moment. Therefore the GP-practices are randomized into one of four groups.

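### Section 4.4 computes 80% power on one-year insured spending, but the steps are two months apart and in-trial control lasts at most 8 months, so the 80% is unsupported for this design

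*Protocol*

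**What the plan says.** Section 4.4 sizes the trial "based on average one year Health Insurance Act spending". It works from "a mean of ca €22.494 (€24.585SD"), "with 80% power, 5% alpha, 2-sided Equality and 25% decrease". It then states: "The unadjusted sample size for a RCT was established on 380, 190 per arm". The multiplier follows: "The design effect for this study is 0.54". Its basis is given next: "This is based on 1 baseline measure, 4 steps, and ICC of 0.1", with 10 patients per cluster and 20% loss. The result is 204, rounded to 200 patients in 20 practices.

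Section 3 fixes the timetable. All practices start control together, a group switches every two months from month 2, and the study lasts 22 months. "The control period varies between 2 to 8 months".

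The Objectives section says: "Primary outcomes: Incremental cost-effectiveness from a societal perspective". Section 5.1.1 names the same main parameter and adds medical data from the three years before the trial. Section 6 gives the trial-based economic analysis a one-year horizon.

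**The concern.** A stepped-wedge design effect converts the size of a simple two-arm trial into the size needed when the same outcome is measured once at baseline and once after each step. The SD and the measurement schedule must therefore refer to the same outcome. Here the SD belongs to a 12-month cost and the schedule is two-monthly. Five separate annual costs would need 60 months, in a study of 22.

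The pre-trial cost data do not close the gap. Section 4.4 does not use them, and they are not a concurrent randomised control. Even if the single baseline were a pre-trial year, the four later measurements would still lie two months apart.

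Shorter cost windows have a larger relative SD, which lowers power. Following the same patients through control and intervention removes between-patient variation, which raises it. Which effect dominates depends on how stable a patient's cost is from one window to the next, and section 4.4 does not address this. At stake is how a null cost result would be read: a reader told that power is 80% for a 25% decrease would give it more weight than the design may justify.

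**Working it through.** **Inputs from section 4.4.** Mean €22,494, SD €24,585, 25% decrease, two-sided 5%, 80% power, ICC 0.1, 10 patients per practice, 20 practices, 20% loss. **From section 3.** Four groups of five practices, two-month steps, 22 months = 11 two-month periods. **Assumed.** Cost is analysed per two-month period. The within-patient correlation r between two-month costs (any two periods) is not given, so a range is shown.

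**1. The plan's design effect reproduces.** With k = 4 steps, b = 1 baseline, t = 1 measurement per step, n = 10 and ρ = 0.1:

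[1 + ρ(ktn + bn − 1)] / [1 + ρ(ktn/2 + bn − 1)] × 3(1 − ρ) / [2t(k − 1/k)] = (5.9 / 3.9) × (2.7 / 7.5) = 0.5446.

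The generalised least squares variance for 20 practices, five periods and no extra patient correlation gives the same 0.5446. 380 × 0.5446 = 207, close to the stated 204. The calculation thus treats the trial as five measurements of the powered outcome.

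**2. A separate discrepancy must be kept apart.** The stated effect is 0.25 × 22,494 / 24,585 = 0.229 SD, which needs 301 per arm (602 in total), not 190. The effect that matches 190 per arm is (1.960 + 0.842) × √(2/190) = 0.287 SD. On annual cost with the plan's own design effect, 200 patients are worth 200 / 0.5446 = 367 in a simple trial. That gives about 59% power at 0.229 SD and 79% at 0.287 SD. The step from 79% to 59% has nothing to do with the time window.

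**3. From annual to two-month cost.** If s² is the variance of a two-month cost, the annual variance is 6s²(1 + 5r). The annual mean is six times the two-month mean. So the two-month CV² is 6/(1 + 5r) times the annual CV²: 4.0, 2.4, 1.71 and 1.33 times at r = 0.1, 0.3, 0.5 and 0.7. The standardised effect per period is the annual one times √[(1 + 5r)/6].

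**4. Closed-cohort power over all 11 periods.** The model has fixed period effects and, in units of s², practice variance 0.1, patient variance r − 0.1 and residual variance 1 − r. The effect is immediate and constant. Power = Φ(effect/SE − 1.96).

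| r | Effect per period (from 0.229) | SE, 10 per practice | Power, 0.229 SD, 10 per practice | Power, 0.229 SD, 8 per practice | Power, 0.287 SD, 10 per practice |
|---|---|---|---|---|---|
| 0.1 | 0.114 | 0.093 | 23% | 20% | 34% |
| 0.3 | 0.148 | 0.082 | 43% | 36% | 62% |
| 0.5 | 0.175 | 0.070 | 71% | 61% | 88% |
| 0.7 | 0.198 | 0.054 | 96% | 91% | over 99% |

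Power reaches 80% at r of about 0.56 (10 per practice) or 0.62 (8 per practice) with 0.229 SD. With 0.287 SD the thresholds are about 0.43 and 0.50.

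**5. Sensitivity.** Setting the ICC of 0.1 on the annual rather than the two-month scale moves these figures by at most about one point. If the effect builds up linearly over the 12 intervention months, power at 0.229 SD with 10 per practice is about 8%, 11%, 16% and 29% at the same four values of r (ICC on the annual scale).

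**The case against.** Four points can be made for the plan.

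- **The mismatch need not cost power.** This stands. With 0.229 SD, 11 periods and 10 per practice, power is 56% at r = 0.4 and 71% at r = 0.5, against 59% on the annual reading. Somewhat above r = 0.4 the closed cohort gives back more than the shorter window takes away. A reader might infer that the trial has less than 80% power. The documents do not support that, because they give no r.
- **Much of any shortfall comes from the starting number.** This also stands, and it is why both effect sizes are shown. A reader who charged the whole gap below 80% to the time window would be wrong. With 0.287 SD the window alone still leaves 34% at r = 0.1 and 62% at r = 0.3.
- **The two-month cost is inferred.** Section 5.1.1 collects record-based costs at months 0 and 22, and the cost questionnaire is given 7 or 8 times on a schedule shown in a figure that is not available here. This limits the figures. It does not rescue the calculation, since any cost interval confined to the in-trial control period is at most 8 months.
- **A cost component may be used for sizing.** It may, and the hypothesis includes lower acute-care spending. A reader might infer that powering on insured spending is itself an error. It is an acceptable choice if stated, but section 4.4 does not say that its power refers to that component only.

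**Conclusion.** The point holds as a mismatch between the outcome used for the power and the measurements the design can supply. The stated 80% is unsupported; it is not shown to be too high. Its true value turns on an undocumented correlation. Across r = 0.1 to 0.7 it runs from about 23% to 96% with the stated mean and SD, and from about 34% to over 99% with the effect size that matches 190 per arm.

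These figures rest on two-month cost periods, equal correlation between any two periods, an ICC of 0.1, use of all 11 periods and an immediate full effect. Section 6 plans a richer model, with separate time trends per practice and a term for time on intervention, so they are indicative only. Power for societal cost per QALY cannot be computed, because the protocol gives no QALY difference, QALY SD, cost–QALY correlation or willingness-to-pay threshold.

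**What to change.** In section 4.4:

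- Name the cost period that the model will analyse.
- Take its mean, SD and within-patient correlation from routine cost data. The plan already draws on Statistics Netherlands for its annual figures.
- Recompute the power of the planned 200 patients with the closed-cohort stepped-wedge variance over the planned periods, with and without the 20% loss.
- State the resulting power, and say that it applies to insured-care cost and not to the primary societal cost per QALY.

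Enrolment stays as planned. The cost is one recalculation and a rewritten paragraph, and the stated power may become less favourable.

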6. STATISTICAL ANALYSIS

Before analysis, all data will be cleaned improving data quality.

Quantitative data:

We will conduct intention-to-treat and per protocol analysis. We will use multilevel generalized linear models with the patient as the first level to correct for the repeated measures. The GP-practice (or cluster) will be the second level, and the group in which the GP practice is randomized will be the third level. We will adjust for level of integration, neighbourhood, time from start of study (continuous; with an interaction between cluster and time so that each cluster had its own underlying time trend), and total time on the randomised intervention, with time before intervention given as zero (continuous). Based on ICPC-codes used to select eligible patients, we will explore if subgroups can be identified in mainly (chronic) somatic, mainly mental or mainly social problems. Furthermore, analyses/ results will be stratification for sex. The analysis of the implementation will be descriptive.

Cost-effectiveness analysis/budget impact analysis:

The economic evaluation will consist of a trial-based cost-utility analysis (cost per QALY) with a time horizon of one year and a cost-utility analysis with a lifetime horizon (cost per QALY). Both analyses will be performed from a societal perspective. Next to this a Budget Impact Analysis will be performed according to the ISPOR Task Force principles.

Qualitative data:

Qualitative data will be collected through interviews or focus groups with care providers and patients and audiorecording. The interviews and focus groups will be conducted using a topic list based on experience of the pilot (protocol number **NL8223-10216**) and literature, to determine their satisfaction with the new approach.

The collected qualitative data will be analysed using both an inductive and deductive approach. This will be done by first transcribing the data and doing a thematic content analysis. After this, the data will be put into an initial coding book and further analysed until a final coding book is formed. The deductive analysis will be done using the positive health methodology. We will analyze whether positive health topics and techniques are being discussed and applied, as recommended by the methodology.

The audiotapes will be scored by two independent observers using the validated OPTION5 questionnaire.

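### The 0.54 design effect and 80% power in Section 4.4 hold for an immediate on/off effect, not for the 12-month question under the model planned in Section 6

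*Protocol*

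**What the plan says.** **Protocol 4.4 (sample size).** The starting point is a parallel-group size: "The unadjusted sample size for a RCT was established on 380, 190 per arm". The outcome behind that figure is "average one year Health Insurance Act spending of a mean of ca €22.494 (€24.585SD"). Error rates and effect size are given as "with 80% power, 5% alpha, 2-sided Equality and 25% decrease". The stepped-wedge correction follows: "The design effect for this study is 0.54. This is based on 1 baseline measure, 4 steps, and ICC of 0.1". The other inputs are 10 patients per practice and 20% loss. The result is 204, rounded to 200 patients in 20 practices. Delay or growth of the effect, time on intervention and practice-specific trends are not mentioned.

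**Protocol Section 6 (analysis).** The multilevel model is adjusted, among other things, for study time as a continuous variable, "with an interaction between cluster and time so that each cluster had its own underlying time trend", and for "total time on the randomised intervention, with time before intervention given as zero (continuous"). No on/off intervention term is named, and none is ruled out.

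**Protocol Objectives.** The primary goal is to "get insight in the cost-effectiveness after 12 months of working with a proactive, integrated (social) care approach". Section 6 gives the trial-based cost-utility analysis a one-year horizon.

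**Protocol Section 3 (design).** Groups switch at months 2, 4, 6 and 8. Each then has 12 months of intervention, and the study ends at month 22.

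**The concern.** A design effect belongs to a particular model and a particular effect. The one in 4.4 is for a random practice intercept, period effects shared by all practices, and one 0/1 intervention term whose full effect is present at the first measurement after the switch. Section 6 frees the time trend by practice and adds exposure time. The question is put at 12 months.

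The layout sharpens this. The first group switches at month 2 and the last at month 8, so the longest exposure with a practice still in the control condition is 8 - 2 = 6 months. Any statement about months 7 to 12 rests on the modelled time trends.

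Two things are at stake. The reader cannot tell which effect has 80% power. And once a 0/1 term and time on intervention are both in the model, the 0/1 coefficient is only the effect at the switch, and the exposure slope is only the change per month. Neither alone is the 12-month effect.

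**Working it through.** **Step 1: reproduce 0.54.** Inputs from 4.4: b = 1 baseline, k = 4 steps, n = 10, ICC = 0.1. One measurement per step (t = 1) is assumed.

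DE = [1 + ICC(ktn + bn - 1)] / [1 + ICC(ktn/2 + bn - 1)] x 3(1 - ICC) / [2t(k - 1/k)] = (5.9/3.9) x (2.7/7.5) = 0.5446.

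380 x 0.54 = 205 and 380 x 0.5446 = 207, close to the printed 204.

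**Step 2: the same figure from generalised least squares (GLS).** Take 20 practice means with practice variance 0.1 and residual variance 0.9/10, five measurements, common period effects and a 0/1 term. The variance is 0.01089. An individually randomised trial of 200 has 4/200 = 0.02, and the ratio is 0.5446. So 0.54 is the design effect of this model and no other.

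**Step 3: power scale.** The standardised difference for which 380 gives 80% power is (1.960 + 0.842) x sqrt(4/380) = 0.2874. Power = Phi(0.2874 / sqrt(0.02 x DE) - 1.96). For DE = 0.5446 this is Phi(0.794) = 79%.

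**Step 4: Section 6 structure.** Same 200 patients, no loss, each practice with its own linear time slope. The documents do not settle the following, so a range is shown:

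- Measurements: either two-monthly to month 22, or months 0, 2, 4, 6, 8 plus 6, 12 and 14 months after the switch. The second is an assumed schedule that gives 7 measurements in the first group and 8 in the others, in line with the protocol's 7 or 8.
- Exposure time: either running on after month 12 or capped there.
- A measurement in the month of the switch counts as control. Counting it as intervention with zero exposure lowers the power of the two-term contrasts.
- The group level and the other covariates are left out.

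| Intervention terms | Quantity | Design effect | Power |
|---|---|---|---|
| 0/1 only | immediate, constant effect | 0.24-0.37 | 98-92% |
| exposure time only | average over 12 months (6 x slope) | 0.36-0.71 | 92-67% |
| 0/1 and exposure time | average over 12 months (0/1 + 6 x slope) | 0.51-1.07 | 81-50% |
| exposure time only | level at month 12 (12 x slope) | 1.44-2.84 | 40-22% |
| 0/1 and exposure time | level at month 12 (0/1 + 12 x slope) | 1.51-3.09 | 38-21% |

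In the exposure-only rows, the 12-month average is half the month-12 level, so its variance is one quarter: 2.01/4 = 0.50 for two-monthly, uncapped data, with power 82%. If a further within-patient correlation of 0.3 is assumed, the two year-average rows become about 64-98%.

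**Step 5: reading one coefficient alone.** If the truth were an immediate, lasting effect and exposure time were the only intervention term, 12 x slope would estimate -0.8 to +0.5 times the true effect. The protocol does not say that it is the only term. The figure shows why the contrast has to be named.

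**The case against.** The strongest reply is that no printed number is wrong. The 0.54 reproduces, 200 patients stand, and a constant effect is the usual sizing assumption. Practice-specific trends alone do no damage: with a 0/1 term and all the data to month 22, power for an immediate effect is 92-98%, above the formula's 79%. That stands, and it means the trends by themselves do not invalidate 0.54.

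A reader might infer that the protocol expects the effect to build over 12 months. It does not say so. The objective gives a horizon, and Section 6 lists time on intervention among the adjustment variables. Intake, team meeting, care plan and at least three contacts in the first 12 weeks (Section 4.5) give some reason to doubt a full effect at the first measurement, but no shape is stated.

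A reader might also infer that power collapses to 21-40%. This needs the 25% to be the level at month 12. Section 4.4 defines it as a decrease in one-year spending, and Section 6 uses a one-year horizon. Under a linear rise, 25% at month 12 means only 12.5% over the year, half the stated effect.

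Finally, the choice of primary contrast may be left to a statistical analysis plan. That is fair, but it does not remove the mismatch: the protocol states both a power basis and a model, and the two do not belong together.

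**Conclusion.** The point holds as a mismatch between 4.4 on one side and Section 6 with the objective on the other. The 80% belongs to a constant on/off effect in a simpler model and is not the power of the planned analysis for the 12-month question. It does not follow that the trial is badly underpowered. For the one-year effect that 4.4 describes, the results lie on both sides of 80%, and they move with the assumed effect shape, measurement schedule, cap on exposure and within-patient correlation.

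All powers above take the 380 as correct. How it was derived is a separate matter. On the stated mean, SD and decrease, the standardised effect is 0.25 x 22,494 / 24,585 = 0.229, and the formula's own model then gives Phi(0.229/0.1044 - 1.96) = 59%, so every figure in the table would be lower.

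This should be corrected, but it does not threaten the design.

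**What to change.** **Section 4.4.** State that 0.54 and 80% refer to an immediate, constant effect with common period effects. Then print the power for the one-year effect under the Section 6 model for the same 200 patients, with the assumed effect shape, measurement times, handling of exposure after month 12 and within-patient correlation.

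**Section 6.** Say whether a 0/1 term is in the model and name the primary contrast. One choice is the average effect over the 12 intervention months, formed from the 0/1 and time-on-intervention terms (0/1 + 6 x slope if exposure is linear in months). Add that neither coefficient alone is to be read as the 12-month effect. If the contrast is defined in a statistical analysis plan, a cross-reference from 4.4 is enough.

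**Cost.** One recalculation and two short paragraphs, and possibly a less favourable stated power. No extra patients, visits or data.
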